To evaluate the safety and acceptability of the ShangRing for device-based circumcision in routine clinical settings, as a part of a comprehensive HIV prevention program for males aged 13 and older in Tanzania.

Evaluation Objectives

The specific objectives of the proposed implementation pilot is to:

- Describe/assess the safety of the ShangRing device by the occurrence of clinical adverse events (calculated as a rate), when circumcision is performed by trained mid-level providers;
- Ascertain capacity and required clinical capabilities of clinical staff of various cadres to carry out ShangRing procedures;
- Describe/assess male client and provider acceptability of the ShangRing device and process (e.g. need to return to the clinic for device removal, tolerance for leaving device in situ);
- Assess the percentage of clients clinically healed 6 weeks (42 days) following the removal of the device;
- Determine the time at which point all clients are physically healed following the removal of the device.

Primary Endpoint

The primary endpoint related to the goal and objectives of the evaluation is to:

- Measure the incidence of mild, moderate and severe AEs associated with ShangRing procedures including both procedure and post-procedure events, and all device-related malfunctions such as early spontaneous displacement. The primary endpoint will be assessed at device placement, at device removal, 3-days post removal, at the day 49 post-placement healing assessment, and at any unscheduled visit in that time frame. Adverse events will be measured and described in the following ways:
 - Total numbers and types of known AEs occurring among clients, including all severities of AEs (mild, moderate, severe) and serious AEs (see below), including detailed information about all instances of device displacement/detachment/self-removal/malfunction, need for medical attention or intervention, and final outcomes in those experiencing AEs.
 - Total number of clients with known AEs (may be different from above if clients experience multiple AEs), including all severities of AEs and serious AEs.

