Potential clients will receive a medical history screening and a genital examination conducted by the VMMC provider to determine that they are in overall good physical health. Additional inclusion criteria include the following:

- Male aged 13 years and older
- Uncircumcised following physical assessment
- Seeking medical circumcision at one of the evaluation sites

- Consents to an HIV test.
- Agrees to be circumcised using the ShangRing device
 - Those aged 13-17 years will also require parental/guardian approval in order to be included in addition to providing assent. Parents must also agree to be present at the facility during the circumcision (though not in the operating room unless requested by the client), for the discharge instructions, and for subsequent follow-up visits.
- Penis fits into one of the 18 ShangRing ring sizes
- Able to understand the evaluation procedures and requirements
- Agrees to abstain from sexual intercourse and masturbation, for six (6) weeks post removal, seven (7) weeks total
- Lives within 30 kilometers of the facility in Shinyanga, Tanzania
- Willing to provide valid contact information (i.e. telephone number, address of residence, place of employment and other locator information) and willing to receive communications and/or follow-up visits, clients may also be asked for names of relatives or friends to be contacted in the event that the client cannot be reached
- Has an activated cell/mobile phone or access to a cell/mobile phone
- Agrees to return for a follow-up visit to assess healing day 49 post-placement (42 days post-removal).
- If not healed at the day 49 post-placement visit, agrees to return for weekly follow up visits until healed.
- Agrees to a 10 day post-placement (3 days post-removal) telephone call to assess and detect symptoms of AEs
- Able to communicate in English and/or Swahili
- Capable and willing to provide written informed consent (18 years and older), or written informed consent from a parent guardian (13-17 years) to participate for both HTS and VMMC services.

Client Exclusion Criteria

Clients who do not meet the inclusion criteria above and who have the following known medical conditions will be excluded from the evaluation:

- Cognitive impairment that prevents the client from providing consent

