The primary focus of the acceptability component of the evaluation is to document attitudes towards and experiences with device circumcision (e.g., acceptability during the procedure and post-operatively during healing period while the device remains *in situ*), effects on activities of daily living, attitudes towards protection from HIV, effects on sexual satisfaction and/or penile sensation and behavior, pain, and satisfaction with cosmetic final result. Perceived acceptability of female partners will be assessed through male clients. The evaluation team will also collect data on reasons for not accepting the device by administering a brief survey to males declining participation in the evaluation (see Appendix XII). Provider acceptability will be assessed by exploring attitudes towards and experiences with device circumcision, impact of offering circumcisions on

clinical practice, barriers and facilitators of clinicians' implementation of device circumcisions (consistency of the final result, simplicity or ease of use).

All men (n=575) who are circumcised during the main implementation phase will be asked to answer a phone call to assess AEs three days post device removal (day 10). All men (n=575) will be asked to return for a follow-up visit on day 49 post-placement to assess healing. All men who are not clinically healed on the day 49 post-placement visit will be asked to return to the clinic at weekly intervals until healed. During the day 49 visit, and subsequent healing visits, men will also have their genital area photographed. A selection of 50 male clients will be asked to participate in private face-to-face qualitative interviews 28 days post-procedure. All clients returning for the day 49 healing assessment, and subsequent healing visits (and for clients under 18 a parent/guardian accompanying them), will be compensated a small amount for their travel costs and time (estimated to be between 7-10 USD/16,000-22,000 Tanzanian Shillings per visit, but not to exceed 30 USD/68,000 Tanzanian Shillings) total, as will clients selected for the face-to-face qualitative interviews (see Reimbursements section). As noted above, providers will be interviewed at the evaluations midpoint, at least after four weeks of client enrollment, and this interview will assess provider satisfaction with training, as well as provider acceptability.

Healing Component

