All clients in the evaluation will be followed up at three points in time following ShangRing circumcision, on day 7 (device removal), on day 10 (three day post-removal AE assessment phone call), and day 49 (42 days/6 weeks following device removal). Ten percent of all clients will be brought in on day 28 (21 days/3 weeks following device removal) for in-depth qualitative interviews.

At the day 49 visit, a clinician will assess healing, an evaluation staff will photograph the client's genitals to document healing, and the client will receive counseling that will stress the following messages:

- If the wound is considered to be healed, the client will be informed that they may resume sexual activity and masturbation, but counseled on the need to continue safe sexual practices.
- If the wound is not considered healed, the clinician will offer ask the client to return in one weeks' time to assess healing and ensure the wound is fully healed. The client will also be advised to continue abstention from sexual activity and masturbation.
- If the client is not considered healed, and there is a clinically indicated reason to schedule further follow-up to take place before the next weekly visit, the evaluation staff will schedule such follow-up visits at a medically appropriate time.
- All sexually active clients will be offered a package of condoms to take home.

One week preceding the day 49 healing assessment visit (day 42) the client will receive a short reminder text asking that the client contact the site to confirm the appointment. The reminder text message will include client name and specify the name and phone number of the clinic reaching out to him. The text message will not include the purpose of appointment visit for which the reminder is sent. The client will be asked to confirm the appointment by either calling the clinic, or by replying with a text. If the client does not confirm the appointment within 3 days, (day 45), the client will be sent a second text. If the client still has not confirmed the appointment by day (47), the client will receive one phone call per day from day 47-49 until they have confirmed the appointment or indicated their intent not to come. If the client does not come in on day 49 for the healing assessment visit, and has not indicated his desire to withdraw from the evaluation, then the client will be established as lost to follow up.

Post Day 49 Healing Assessment Visits

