Excess Skin Removal	C-SD: Excess skin removal —slight tightening of the skin observed; no surgical correction needed.	C-SD: Excess skin removal —pulling of scrotal skin onto the penile shaft and wound disruption.	C-SD: Excess skin removal —wound appearance is such that the wound has gaping edges or large or deep defects such that without revision, there would be significant scar formation.
SX: Sexual Effects/Undesirable Sensory Changes	C-SX: Occasional inability to have erection or dissatisfaction with sexual performance, no psycho-behavioral consequences.	C-SX: Post-operative changes that consistently impair or preclude sexual function for 3 to 6 months after surgery not present prior to surgery.	C-SX: Post-operative changes that consistently impair or preclude sexual function for greater than 6 months after surgery that were not present prior to surgery.
WD: Wound Disruption	C-WD: Wound disruption but not extensive enough to require suturing for wound closure.	C-WD: Muco-cutaneous gap > 1.0 cm in width, but no exposure of deeper tissue	C-WD: Wound disruption exposing tissue deeper than subcutaneous tissue or requiring surgical intervention such as suturing or debridement.
OA: Other AEs, Excess swelling of penis/scrotum including hematoma; other	Excess swelling —mild swelling without signs of on-going bleeding.	
Excess swelling—symptoms/signs that require clinical intervention, but not surgical exploration.
 
Other—other adverse events related to surgery that result in disability (as evidenced by loss of work or cancellation of normal activities) lasting for at least 4 days after surgery but not more than 7 days.
	
Excess swelling—surgical exploration required to control bleeding or remove haematoma or symptoms/signs so extraordinary as to cause disability (as evidenced by loss of work or cancellation of normal activities) lasting for at least 8 days after surgery or device placement or removal as pertinent.

			Other —other AE(s) related to the surgery that result in disability (as evidenced by loss of work or cancellation of normal activities) lasting for at least 8 days after surgery or device placement or removal, or result in hospitalization or referral/transfer to another facility.

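### Moderate and severe sexual-effect AEs cannot be reached by day 49, and the sexual-satisfaction part of the acceptability aim has no time point or survey item to answer it

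*Protocol*

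**What the plan says.** The Primary Endpoint section sets out to "Measure the incidence of mild, moderate and severe AEs associated with ShangRing procedures". The last assessments it lists are "at the day 49 post-placement healing assessment, and at any unscheduled visit in that time frame". The Follow-Up Visits section confirms the schedule: "All clients in the evaluation will be followed up at three points in time following ShangRing circumcision", namely day 7, a day 10 phone call and day 49. Only clients not healed at day 49 have further weekly visits.

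Appendix XIX grades sexual effects and undesirable sensory changes (C-SX) at three levels:
- Mild: occasional erectile difficulty or dissatisfaction with sexual performance, with no minimum duration.
- Moderate: "Post-operative changes that consistently impair or preclude sexual function for 3 to 6 months after surgery".
- Severe: the same kind of impairment lasting more than 6 months.

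The category is a tick box on the device events form in Appendix XVIII.

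The Client Inclusion Criteria require that the client "Agrees to abstain from sexual intercourse and masturbation, for six (6) weeks post removal, seven (7) weeks total". At the day 49 visit, if the wound is healed, "the client will be informed that they may resume sexual activity and masturbation". The Acceptability Component nevertheless lists "effects on sexual satisfaction and/or penile sensation and behavior" among the things to be documented.

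**The concern.** Two parts of the plan ask for information that its schedule cannot supply.

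First, the moderate and severe C-SX grades are defined by durations longer than the period in which the primary endpoint is assessed. The Analysis Overview presents AE rates by severity and analyses the data as they stand. Nothing tells the reader that these two grades could not have been reached. An empty line for them may be taken as a favourable finding, and the results are meant to inform Ministry policy and counselling messages.

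Second, the sexual-satisfaction part of the acceptability aim would be answered by men who have been told to abstain, using surveys that do not ask about it.

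**Working it through.** **Inputs.** Endpoint window: 49 days after placement (Primary Endpoint). Moderate C-SX: at least 3 months; severe: more than 6 months (Appendix XIX). Planned cohort: 575 (Sample Size section). One month is taken as 30.44 days.

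**Plan's own figure.** The protocol gives no figure on sexual effects. Its one precision figure reproduces: n = 1.96² × 0.02 × 0.98 / 0.015² = 334.6, rounded up to 335 as stated. This point leaves it untouched.

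**Window against definition.**
- Moderate: 3 × 30.44 = 91.3 days; 91.3 − 49 = 42.3 days short; 49 / 91.3 = 54% of the minimum duration is covered.
- Severe: 6 × 30.44 = 182.6 days; 182.6 − 49 = 133.6 days short; 49 / 182.6 = 27% is covered.

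**Weekly visits after day 49.** These could carry a client past 3 months only if he stayed unhealed long enough: 42.3 / 7 = 6.04, so the seventh extra visit would be the first beyond that point. Such a client is told to keep abstaining, and these visits are not among the assessments listed for the primary endpoint.

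**What a missed rate could mean.** The documents give no rate for these events. Assuming a true moderate-or-severe rate of 0.2% to 1%, the expected number among 575 clients is 575 × 0.002 = 1.2 to 575 × 0.01 = 5.8, none gradable at moderate or severe by day 49. If someone treated the structural zero as data, the exact two-sided 95% upper limit would be 1 − 0.025^(1/575) = 0.64%. This only illustrates a possible misreading; the plan does not call for that interval.

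**Acceptability instruments against the aim.**
- Post-placement survey, day 0 (Appendix X): reason for choice, placement, pain, recommendation. No item on sexual satisfaction.
- Post-removal survey, day 7 (Appendix XI): discomfort, daily activities, choice of method, appearance, recommendation. No item on sexual satisfaction.
- Interview of 50 clients, day 28 (Appendix XXII): the probe that mentions sex concerns limits during the seven days of wear; later questions ask openly about experience since removal and satisfaction with the circumcision. Day 28 is 49 − 28 = 21 days before a seven-week abstinence period ends, and 42 − 28 = 14 days before a six-week one ends.

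**Abstinence statements side by side.** The inclusion criteria give seven weeks in total. The post-placement counselling section gives 49 days from placement or until healed, whichever is last. The take-home sheet (Appendix XVII) gives six weeks after circumcision or until healed, without saying which governs. These do not agree.

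**The case against.** A reader might infer that the whole sexual-effects category is unobservable and that a zero rate is built in. The documents do not support that. Mild C-SX has no duration, mild events count in the primary endpoint, and the device events form offers the category with a mild grade. Erectile difficulty and sensory change can be reported without intercourse; the counselling sections themselves expect night-time erections. A client following the take-home sheet might also have resumed sex before day 49.

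A reader might also infer that higher grades can never be recorded. The section on AE documentation follows each AE to resolution or a stable endpoint, the section on potential harm continues clinical follow-up beyond six weeks, and unscheduled visits review sexual function where applicable. A complaint recorded early could therefore be regraded later. This stands, but it depends on the client raising the problem by day 49. It is not systematic and would miss trouble first noticed on resuming sex.

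Nor does the plan promise 0 out of 575 with an upper limit of 0.64%. The Analysis Overview attaches its confidence limit to clients with one or more AE, and the Primary Endpoint section reports known AEs by type. Appendix XIX is a general grading table adapted from a guide covering surgery and devices, so some of its grades may outlast any one study.

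On acceptability, the formal client endpoints under Secondary Endpoints and in Table 2 do not name sexual satisfaction, and penile sensation can be reported during abstinence. The gap is confined to one item in the component's stated focus.

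**Conclusion.** The point holds for two C-SX grades and for one element of the acceptability aim. Moderate and severe C-SX lie at least 42 and 134 days beyond the endpoint window, so their absence by day 49 carries no information about safety. Sexual satisfaction after resuming activity cannot be learned from surveys at days 0 and 7 and an interview at day 28.

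The conclusion on the grades needs only the stated durations and the stated window; it does not depend on whether clients comply with abstinence. The conclusion on acceptability assumes that clients broadly follow the abstinence advice and that the appended surveys are those to be used. The overall AE rate, read as a rate to day 49, stands, as does the sample-size calculation. The change is worth making because it costs little and alters what may be concluded from an empty line in the AE table.

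**What to change.** 1. In Primary Endpoint and Analysis Overview, state that moderate and severe C-SX are not systematically ascertainable by day 49. Report them as 'not assessed', not as 0. Keep mild C-SX and sensory changes in the AE summary.
2. List separately any sexual complaint first recorded by day 49 and regraded during AE follow-up, so that no known case is lost.
3. In the Acceptability Component, limit the aim to erection-related comfort and penile sensation during wear and healing, or drop sexual satisfaction.
4. Reconcile the abstinence periods in the inclusion criteria, the post-placement counselling section and Appendix XVII. Which of them should stand is for the clinical team.

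The cost is wording and a slightly narrower stated scope. A phone contact after 3 months, reported apart from the primary rate, is an option if the sponsor wants the information; the fix does not need it.

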Appendix XX - ShangRing Evaluation Pilot: Application Time Form

ShangRing Evaluation Pilot: Application Time Form

(Enter time in 24 hour form, e.g. 18:00)

Overall Time: Begins upon the arrival of client in operating room, concludes once procedure is complete and client is released from operating room.

Appendix XXI - ShangRing Evaluation Pilot: Removal Time Form

ShangRing Evaluation Pilot: Removal Time Form

(Enter time in 24 hour form, e.g. 18:00)

***Begin/End Time:** Time begins when client is admitted to the room for device removal. Time ends when device is removed and client is ready to be released.

Appendix XXII – Client Qualitative Interview Guide

In-Depth Qualitative Interviews

Date (dd/mm/yyyy):	
Name of Moderator:	
Name of Note-Taker:	
Facility:	
Start Time:	
End Time:	

Introduction

Thank you for agreeing to participate in this interview. The purpose of this interview is to discuss your opinions around circumcision and ShangRing. In order to do this, I will ask you questions about your experience with the ShangRing device for male circumcision. This interview, and your replies will be kept completely confidential. I will not record your name or link anything you say in a way that will make it easy to identify you. In this interview there are no right or wrong answers. We are most interested in your honest opinions and reactions to these questions. You may also refuse to answer any question you wish for any reason. The interview should last approximately one hour, though you may end it at any time. The interview will be recorded, but your name will not be included on the recording, and we will not store the recording in a way that can be used to identify you. You may request a break should you need one. Please feel free also to help yourself to the provided snack. And if you need them, the rest rooms are located [provide directions]. The information that you and others provide will help to determine the future use of ShangRing in Tanzania.

Are there any questions before we begin?

1. How old are you in complete years?
2. Where do you currently reside?
3. What is the highest level of formal schooling you completed?
4. Are you currently in a relationship with someone such as a spouse or partner? [Note for interviewer: if yes ask question 5, if no, skip to question 6].
5. What is your relationship with this person?
6. What was the primary reason you decided to get circumcised?
7. What made you decide to try the ShangRing device?
8. What made you choose to try the ShangRing device instead of surgical circumcision?
9. Did you tell anyone that you had a ShangRing circumcision? If so, what was their reaction? [Note for interviewer: probe for who the person was, gender, relationship to the client, etc.].
10. How was the process of having the ShangRing device put on your penis?

11. What was it like during the seven (7) days that you had the device on? [Note for interviewer: probe for issues related to pain including with erections, limits on activities including sex and masturbation, hygiene].
12. How was the removal process?
13. What have you been told about the healing process? [Note for interviewer: probe for things they have been told to do and what not to do until healing is complete. *Clarify any information that is not correct regarding abstinence until healing is complete and future condom use*].
14. How would you describe your experience since the ShangRing device was removed? [Note for interviewer: probe for perceptions regarding how the healing process is progressing].
15. How would you describe your satisfaction with your circumcision?
16. Are you satisfied with the result?
17. What did you like about the procedure?
18. What did you dislike?
19. Was the information about the circumcision process with the ShangRing device clear and accurate?
20. In your opinion, what kind of messages could make VMMC more appealing to men?
21. In your opinion, are there messages that could make ShangRing an appealing option for VMMC for men who may not want to have surgery?
22. Is there anything else related to ShangRing that you would like to comment on or ask?
23. Do you have any comments related to ShangRing or medical male circumcision in general?

Note for Interviewer: Thank the client for their time, and provide the following reminders:

- When/where to return for the day 49 (42 days post-removal) healing assessment.
- The importance of good hygienic processes while the wound continues to heal, and how to keep the penis and wound clean and free of potential infection, including the importance of tetanus mitigation strategies.
- That the client should return to the evaluation site in case of any unexpected event, for example if there is severe discoloration of the penis, signs of infection (purulence), severe or increasing pain, or any other significant concern they may have.
- Painful erections may continue to occur during the night as the wound heals.
- The client is encouraged to call any time with any questions or concerns.
- The importance of continued abstention from sex or masturbation for 6 weeks (42 days), following the removal of the ShangRing device, or until the penis is fully healed (whichever comes last).

